6.2 Analysis Populations - Current

Enrolled Population: All patients who have provided an informed consent are included.

Safety Population: The Safety Population consists of all patients who receive at least one dose (or partial dose) of study drug (NKTR-102) under this study.

6.3 Analytic Definitions

General:

- Age: integer of (Date informed consent signed (Current)– Date of birth) / 365.25.

- Study Day 1: Day 1 is the date of Cycle 1 Day 1 dosing date within Current study.
- Baseline (Current): Baseline will be defined as the last non-missing assessment on or before the study drug administration (Day 1).
- Study day of Current: For post-treatment events, study day is calculated as (visit/assessment date – date of current study first dose of cycle 1 study drug administration) + 1. For pre-treatment events, study day is calculated as visit date – date of Day 1. There is no study day zero.
- Study Day since First Dose of Original NKTR-102: study day is calculated as (visit/assessment date of current study – date of 1st dose of the original NKTR-102 study) + 1.
- Study Day since Last dose of Original NKTR-102: study day is calculated as (visit/assessment date of current study – date of last dose of the original NKTR-102 study) + 1.
-

Exposure

Current:

- Exposure Duration (days): Date of last dose – date of first dose (Cycle 1 Day 1) of current study + 21.
- Number of cycles: Total number of complete or partial treatment cycles the patient received.
- Cumulative dose (mg): Total actual dose (mg) the patient received across all cycles, defined as the sum of actual dose (mg) received across all cycles.
- Duration of infusion: Completion time of infusion – start time of infusion.
- Calculated cumulative dose level (mg/m^2): Cumulative dose (mg) divided by the average BSA (m^2) across all cycles.
- Dose intensity ($\text{mg}/\text{m}^2/\text{week}$): $[\text{Calculated cumulative dose level } (\text{mg}/\text{m}^2) / \text{exposure duration (days)}] \times 7$.
- Expected dose intensity ($\text{mg}/\text{m}^2/\text{week}$): initial planned dose (mg/m^2) / 3; planned dose will be 145, 120 or 95 mg/m^2 .
- Relative dose intensity (%): $\text{Dose intensity } (\text{mg}/\text{m}^2/\text{week}) / \text{Expected Dose intensity } (\text{mg}/\text{m}^2/\text{week at enrollment}) \times 100$.

Overall (Original plus Current):

The exposure duration, number of cycles, cumulative dose, calculated cumulative dose level from 1st dose exposure of the original NKTR-102 study to last exposure of current study will also be calculated.

6.4 Handling of Missing Data

- If AE is marked as continuing from prior study as recorded in the CRF and Start day of AE is missing, no imputation will be done, otherwise:
 - Missing day of month will be imputed as the first of the month. Missing month will be imputed as July if the year is before Day 1.
 - If the reported month of occurrence of AE is after the month of Cycle 1 Day 1 dose then day will be imputed as the first day of the month of occurrence of AE.
 - If the reported month of occurrence of AE is the month of Cycle 1 Day 1 dose then the missing day will be imputed as the same day as Cycle 1 Day 1.
- For duration of AEs, partially or completely missing dates for stop of AE, will be imputed as follows:
 - Missing day, month, and year are not allowed and should be queried. In case of non-resolution of missing month and/or year, no imputation will be performed.
 - If the day and/or month is missing, but year is present, the last day of that month and December, the date of discontinuation from the study, or the date of death, whichever is earlier, will be used as the stop date.

No imputation of other missing data is planned.

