### 5.1 Inclusion Criteria

Each subject must meet the following criteria to be eligible for enrollment.

1. Subject or subject's legal representative must provide written informed consent.
2. Subject is able and willing to comply with the study visit schedule and procedures.
3. Subjects must have received prior treatment with NKTR-102 in a Nektar-sponsored study.
4. Subjects must be without signs of disease progression since receiving NKTR-102.
5. Women of childbearing potential must have a negative serum pregnancy test at screening and a negative urine pregnancy test at the predose visit of each cycle.
6. Women of childbearing potential and men who agree to use adequate contraception during study participation (at least two methods of contraception, one of which includes a barrier method [male condom] by the male partner or abstinence) or a male who has undergone a vasectomy greater than 6 months prior to Cycle 1 Day 1. Appropriate contraception must be used for at least 8 months after the last dose of the study drug on this extension study.
7. Subjects must meet requirements with respect to hematopoietic function (hemoglobin  $\geq 8.0$  g/dL or 80 g/L; absolute neutrophil count (ANC)  $\geq 1.5 \times 10^9$ /L; platelets  $\geq 75 \times 10^9$ /L).
8. Subjects must be able to receive the first dose of NKTR-102 in the extension study within 8 weeks after receiving their last dose of NKTR-102.

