### 9.2 Monitoring Adverse Events

All AEs will be assessed by the Investigator and recorded in the appropriate case report form (CRF), including but not limited to, the date of onset and resolution, seriousness, severity, relationship to study drug, outcome, and action taken with study drug. Adverse events will be reported starting immediately after the subject or subject's legal representative has provided written informed consent through the End-of-Treatment visit (30 ± 7 days from the last dose of study drug in the extension study).

After providing informed consent for the extension study, if the subject is continuing in the original protocol and therefore will not have received the first dose of study drug in the extension study (Protocol 11-PIR-09), any AEs that occur will be collected under the original protocol. For subjects who have ended the original protocol and have provided informed consent for the extension study (Protocol 11-PIR-09), AEs will be collected under the extension study (Protocol 11-PIR-09).

Adverse events that were considered related to study drug in the original protocol and were ongoing when the subject ended the original protocol will be captured as a new AE in the extension study (Protocol 11-PIR-09) marked as continuing. Unrelated AEs that were ongoing at the end of the original protocol may also be captured as new AEs in the extension study (Protocol 11-PIR-09) marked as continuing.

For each AE, the following data elements will be recorded on the CRFs:

- Verbatim description of event
- NCI-CTCAE v. 4.0 grade for AE severity (refer to Section 9.3)
- Start and stop date of AE
- Relationship/causality attribution to study drug
- Whether or not the administration of study drug was reduced, interrupted, delayed, or permanently discontinued due to the AE
- Whether or not the event was considered as an SAE
- Treatment provided for the AE (pharmacologic or non-pharmacologic)
- Outcome of the AE

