4.0 STUDY ENDPOINTS

4.1 Endpoint

- Incidence and duration of toxicities, with severity grading according to NCI-CTCAE v 4.0.
- Tumor response per Response Evaluation Criteria in Solid Tumors (RECIST) version 1.1.

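### SAP 6.4 puts no lower bound on imputed adverse-event start dates: some imputed onsets are impossible, and AEs with partial dates after the Cycle 1 Day 1 month are lengthened

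*SAP*

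**What the plan says.** SAP 6.4 treats partial AE dates as follows.

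- **Continuing AEs.** An AE marked on the CRF as carried over from the prior study, with its start day missing, is not imputed. The start rules below therefore apply to other AEs.
- **Start, general.** "Missing day of month will be imputed as the first of the month. Missing month will be imputed as July if the year is before" that of the first extension dose.
- **Start, month after the Cycle 1 Day 1 month.** A missing day again goes to the start of the month: "then day will be imputed as the first day of the month of occurrence of AE".
- **Start, Cycle 1 Day 1 month.** A missing day becomes the dosing date.
- **Stop.** "If the day and/or month is missing, but year is present, the last day of that month and December, the date of discontinuation from the" trial; death is a further limit, and the earliest of these is used. Missing parts of a stop date are to be queried first.

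No rule ties an imputed start to consent, to the end of the original protocol or to the AE's own stop date.

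The protocol limits which AEs belong to the extension. Section 9.2 says: "Adverse events will be reported starting immediately after the subject or subject's legal representative has provided written informed consent through the End-of-Treatment visit". The same section assigns AEs that occur while the subject is still on the original protocol to that protocol. Section 7.1 places the screening visit, which includes consent, within 28 days before Cycle 1 Day 1. Section 5.1 requires: "Subjects must be able to receive the first dose of NKTR-102 in the extension study within 8 weeks after receiving their last dose of NKTR-102".

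Duration is part of the endpoint in SAP 4.1: "Incidence and duration of toxicities, with severity grading according to NCI-CTCAE v 4.0". The protocol synopsis names it in the primary endpoint.

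**The concern.** An imputed date should at least be a date on which the event could have happened. Two of the start rules do not guarantee this for an AE that begins before the first extension dose. For later AEs, the start moves to the earliest possible day and the stop to the latest day the rule allows. The imputed duration is then the longest the record permits, not an estimate of it.

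The toxicities at issue are short. The protocol reports median times to resolution of diarrhea in the prior Phase 3 study of 1.5 days (all grades, Section 2.1.2.5), 3.5 days (Grade 2 or higher) and 6 days (Grade 3, both Section 6.8). A shift of two weeks or more in a few records could set the longest duration and raise the mean for a preferred term. Protocol 2.2 gives long-term exposure as the reason for collecting safety data here.

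**Working it through.** The plan states no expected duration or share of partial dates, so there is no figure of its own to reproduce. The check applies the rules by date arithmetic. Assumptions: duration = stop − start + 1 (the SAP gives no AE duration formula); July is combined with day 1; the true day is uniform within its month.

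**1. July rule.** A non-continuing AE belongs to the extension only after extension consent and after the original protocol has ended.
- Lower limit from the 8-week dosing gap: Cycle 1 Day 1 − 56 days. From the screening window: Cycle 1 Day 1 − 28 days.
- For the onset year to precede the Day 1 year, the earliest case is a first dose on 1 January: 1 January − 56 = 6 November; 1 January − 28 = 4 December. The latest possible onset is 31 December.
- Days from 1 July: to 6 November 128, to 4 December 156, to 31 December 183.
- Even 31 July is 98 (126) days before the earliest possible date, so the choice of day does not matter.
- Reach: first doses from 1 January to 25 February only (25 February − 56 = 31 December), or to 28 January with the 28-day window.

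Example: first dose 1 January 2014, consent 4 December 2013, start known only as 2013, stop 20 December 2013. Imputed: 1 July to 20 December = 173 days. Longest true duration: 4 to 20 December = 17 days. The excess is at least 156 days; one such record among 10 for a preferred term adds 156/10 ≈ 16 days to the mean.

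**2. First of the month, before the Cycle 1 Day 1 month.** Take every first-dose date in 2014 and 2016 with consent 1 to 28 days earlier and in the preceding month. Each month gives 28 + 27 + … + 1 = 406 combinations, so 24 × 406 = 9,744. The first of that month precedes consent in 9,743. The exception is a first dose on 1 March 2014 with consent on 1 February. Example: consent 20 March, first dose 5 April, AE dated March gives 1 March, 19 days before consent.

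**3. Months after the Cycle 1 Day 1 month.** In a month of L days the mean shift is (L − 1)/2: 13.5 days (L = 28), 14.5 (L = 30), 15.0 (L = 31), or 14.7 averaged over the days of a year. The maximum is 30. This holds for a missing start day, and for a missing stop day when the discontinuation or death cap is not reached. With both days missing in one 30-day month, a true 2-day AE becomes 30 days.

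**4. Overall mean.** Added mean = share × 14.7 days. The shares are assumed. The true mean is 1/(1 − exp(−ln 2/median)) for exponential durations rounded up to whole days: 2.7 days for a median of 1.5 and 9.2 days for a median of 6.

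| Share with one imputed end | Added mean (days) | Median 1.5 | Median 6 |
|---|---|---|---|
| 2% | 0.3 | 11% | 3% |
| 5% | 0.7 | 27% | 8% |
| 10% | 1.5 | 55% | 16% |

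**The case against.** The case for leaving the rules alone has real content.

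- **Rarity.** The July rule needs a non-continuing AE between consent and first dose, across a year end, with the month unknown. That stands. Such records also stay before the first dose, so a reader who inferred that incidence or pre-dose status is misclassified would be wrong.
- **Inflation is not universal.** It is tempting to read SAP 6.4 as inflating AE durations throughout the study. The documents do not support this. Stop dates are capped and missing parts queried first, and one line of SAP 6.4 leaves an unresolved missing stop month without imputation. The Cycle 1 Day 1-month rule can shorten a duration: with the first dose on the 20th and an AE on the 8th to 10th with its start day missing, the result is 10 − 20 + 1 = −9 days.
- **The first of the month is not always impossible.** For months after the Cycle 1 Day 1 month it is merely the earliest possible day. It becomes impossible only before that month, and the near-certainty there depends on consent falling in the 28-day window.
- **Reporting.** The SAP text supplied ends at Section 7.6 and shows no AE analysis section. That a mean and maximum will be reported rests on the general rule in SAP 6.1; Protocol 12.2 says only that duration is tabulated. SAP 6.1 also gives the median, and no hypothesis test is planned.
- **Convention.** Earliest start with latest stop is a defensible bound for safety data. It should then be labelled as a bound.

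None of this rescues the July rule, which has no case in which it gives a possible date.

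**Conclusion.** The point holds in a limited form. For AEs not marked as continuing, the July rule is wrong by 128 to 183 days (156 to 183 with the screening window) whenever it applies. The first-of-month rule before the Cycle 1 Day 1 month almost always gives an onset before consent. These records are few; only their durations suffer. For later months, each imputed end adds about 15 days on average to the affected AE.

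This assumes that the eligibility and screening windows are kept, that onset days are uniform within the month, and, for stops, that the cap does not bind. The overall effect cannot be settled from the documents: under assumed shares of 2% to 10% with one imputed end, the mean rises by about 0.3 to 1.5 days. The median hardly moves. It is worth correcting because duration is part of the endpoint and the correction is cheap.

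**What to change.** In SAP 6.4:

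1. Delete the July rule.
2. For a non-continuing AE with a partial start before Cycle 1 Day 1, impute the latest of extension consent, the end of the original protocol and the first day of the known period, and never a date after the AE stop. Consent alone is not a sufficient floor, because Protocol 9.2 leaves AEs that occur while the subject is still on the original protocol with that study.
3. Keep the rest of the existing imputation for ordering events.
4. Report AE duration twice: with imputed dates, labelled as an upper bound, and without AEs whose start or stop was imputed. Give the number affected. The label does not fit starts set to the dosing date in the Cycle 1 Day 1 month, which can be too late; footnote these.
5. Keep unresolved AEs in view, counted separately or treated as censored. A summary limited to complete start and stop dates would drop them, and they are likely to include the longest toxicities.

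The cost is a few lines of SAP text and one extra summary row, with no new data collection.

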## 9.5 Adverse Event Reporting and Follow-up

All AEs will be followed until resolution or until  $30 \pm 7$  days after last dose of study drug administration, whichever is earlier, except related AEs which will be followed until they stabilize or resolve; until the Investigator assesses the event as chronic or stable; start of new cancer therapy; subject lost to follow-up or subject death, whichever is earlier. If an unrelated AE has not completely resolved up to  $30 \pm 7$  days after last dose of study drug, the final outcome of these ongoing AEs will be captured as “Not Recovered/Not Resolved” or “Recovering/Resolving”, whichever is applicable.

Any new AEs occurring more than  $30 \pm 7$  days after last dose of study drug will be captured only if serious and assessed by the Investigator as related (possibly/definitely related) to study drug (i.e. a related SAE). For specific instructions on identifying and reporting SAEs, see Sections 9.6 and 9.7 below.

This study will use the MedDRA for coding all AEs.

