### 12.2 Endpoints and Planned Analyses

The primary endpoint of this study is assessment of safety for subjects receiving continued NKTR-102 therapy.

The MedDRA medical dictionary will be used to map the AE/SAE verbatim terms to specific system organ classes and preferred terms. The incidence and duration of AEs will be tabulated by MedDRA preferred term, system organ class, severity and relationship to study drug. The maximum intensity and frequency of AEs will be summarized by treatment (dose level). By-subject listings will be provided. No formal statistical testing is planned for AE or other safety and tolerability data.

Tumor response will be summarized by histological tumor type and tabulated using by-subject listings based on disease assessments from this protocol.

Other data will be tabulated using by-subject listings.

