6.0 STATISTICAL CONSIDERATIONS

6.1 General Considerations

Summary statistics for continuous variables will include the mean, standard deviation, median, and range (minimum and maximum). The mean and median will be presented to one decimal place beyond which the data were captured. The standard deviation will be presented to two decimal places beyond which the data were captured. The minimum and maximum will be presented to the precision with which the data were captured.

Categorical variables will be presented as frequency counts and percentages. A row or column denoted 'Missing' will be included in count tabulations where necessary to account for dropouts and missing values. Percentages will be rounded to 1 decimal place and the percent will be suppressed when the count is zero. The denominator will be the number of patients in that dose schedule within the population of interest unless otherwise noted.

All analyses will be summarized for all patients (Total) and by dose level if sample size allows. Data listings will be created to support each table and to present all data. Data listings will be presented by subject number (combination of original NKTR-102 study ID, subject and site ID).

Neither hypothesis testing nor a specific sample size is required for this study.

We will use the term "Original NKTR-102" when referencing the study where a subject first exposed to NKTR102 before rolling over to current study, "Current" to indicate 11-PIR-09 (extension) study and "Overall" to indicate information inclusive of the original NKTR-102 and current throughout this document. The default implication is "Current", when no study specific information is specified,.

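### SAP 6.4 can place an imputed AE start after a known stop date, its two stop-date rules conflict, and no visible rule covers the duration of AEs still ongoing

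*SAP*

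**What the plan says.** **Endpoint.** SAP 4.1 lists "Incidence and duration of toxicities, with severity grading according to NCI-CTCAE v 4.0", and the statistical methods in the protocol synopsis call this the primary endpoint. Protocol 12.2 adds: "The incidence and duration of AEs will be tabulated by MedDRA preferred term, system organ class, severity and relationship to study drug". SAP 6.3 gives no formula for AE duration.

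**Start dates (SAP 6.4).** A missing day becomes the first of the month. If the AE falls in the month of Cycle 1 Day 1, "then the missing day will be imputed as the same day as Cycle 1 Day 1". AEs marked as carried over from the prior study are exempt.

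**Stop dates (SAP 6.4).** Missing parts are to be queried. "In case of non-resolution of missing month and/or year, no imputation will be performed". The next bullet covers a missing day or month with a known year: the stop becomes the earliest of the period end (month end or December), study discontinuation and death. The section closes by ruling out any other imputation.

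**Collection and follow-up.** Protocol 9.2: "Adverse events will be reported starting immediately after the subject or subject's legal representative has provided written informed consent". For a subject still in the original study, AEs before the first extension dose belong to that study. Protocol 7.1 allows screening up to 28 days before dosing. Under Protocol 9.5, if an unrelated AE is still open at 30 ± 7 days after last dose, "the final outcome of these ongoing AEs will be captured as" either not resolved or resolving. Related AEs are followed longer, but may also be closed as chronic or stable, at new cancer therapy, at loss to follow-up or at death.

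**The concern.** The start rule presumes that an AE in the dosing month began on or after dosing. The protocol collects AEs before dosing, so that need not be so. When it is not, the record holds an impossible date order, a duration of zero or less, and a pre-dose event placed on study Day 1.

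The second issue is a gap. An AE with no stop date because it has not ended has no computable duration. A mean or median over the rest describes resolved events only, and longer events are more likely to be unresolved. Protocol 2.2 says this trial may give the longest exposure to NKTR-102 so far, so persistent toxicities are where an accurate duration matters most.

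**Working it through.** The plan has no figure to reproduce: "Neither hypothesis testing nor a specific sample size is required for this study".

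**1. Start rule, worked example.** Assume dosing on 20 March, an AE from 5 to 10 March with the start day missing, and a subject who has left the original study and consented to this one. 5 March is 15 days before dosing, inside the 28-day window. Because SAP 6.3 defines no duration formula, both usual forms are shown.

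- True: 10 - 5 + 1 = 6 days.
- SAP 6.4: start = 20 March, so 10 - 20 + 1 = -9 days (or -10 without the +1).
- Study day of onset becomes 1, although the AE ended 10 days before dosing.

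**2. Start rule, all cases.** Take every dosing date in a 365-day year and every stop date in the same month, before dosing and within 28 days of it. This gives 5,348 combinations.

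- With the +1: 4,995 negative (93.4%) and 353 zero (6.6%); the lowest is -27.
- Without the +1: all negative; the lowest is -28.
- With the start set to the earlier of Cycle 1 Day 1 and the stop date: every duration is at least 1 day.

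These are shares of calendar combinations once the situation arises. They do not say how often it arises.

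**3. Stop-date bullets.** Suppose an AE starts on 10 February and the stop has a year (the same, non-leap) but no month. The first bullet gives no stop date and no duration. The second gives 31 December, unless discontinuation or death is earlier: 365 - 41 + 1 = 325 days. One record thus yields nothing or up to 325 days, depending on which bullet is followed.

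**4. Ongoing AEs, if only resolved ones are summarised.** The assumptions are exponential durations with median m, onset uniform over T days of treatment, and observation to day T + 30. T = 730 matches the roughly 2 years of treatment in Protocol 6.6; 105 (five 21-day cycles) and 180 are assumed shorter periods. With λ = ln 2 / m, time under observation after onset is uniform from 30 to T + 30 days, so

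unresolved share = [exp(-30λ) - exp(-(T+30)λ)] / (λT).

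For m = 60, λ = 0.01155:

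- T = 105: (0.7071 - 0.2102) / 1.213 = 0.41
- T = 180: (0.7071 - 0.0884) / 2.079 = 0.30
- T = 730: (0.7071 - 0.0002) / 8.433 = 0.08

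The resolved-only median is the x at which F(x), the probability that an AE resolves under observation within x days, is half the resolved share. For x above 30,

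F(x) = 1 - exp(-λx)(T+30-x)/T - [exp(-30λ) - exp(-λx)]/(λT).

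Check for m = 60, T = 105, x = 30.3: F = 0.295, and half the resolved share is 0.590 / 2 = 0.295. For x up to 30, F(x) = 1 - exp(-λx).

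| True median (days) | T = 105: unresolved; median | T = 180: unresolved; median | T = 730: unresolved; median |
|---|---|---|---|
| 6 | 0.26%; 6.0 | 0.15%; 6.0 | 0.04%; 6.0 |
| 30 | 19%; 23 | 12%; 25 | 3%; 29 |
| 60 | 41%; 30 | 30%; 38 | 8%; 53 |
| 90 | 54%; 34 | 43%; 44 | 14%; 74 |

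Kaplan-Meier with censoring recovers the assumed median in simulation (for T = 180: 30.1 for 30 and 89.9 for 90). That is expected, because censoring is independent of duration by construction.

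**The case against.** **The gap on ongoing AEs is inferred from silence.** The SAP text available stops at 7.6, without a safety section or the table shells. A censoring rule may be there. This stands, so the point is conditional. A reader might take the non-resolution clause in 6.4 to exclude unresolved AEs by rule; it refers to a data query that was not answered.

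**The 30-day cut-off does not apply to related AEs.** Protocol 9.5 follows them further, and Protocol 7.4 asks about their resolution every quarter. This stands, and the table overstates the effect for related AEs that are followed to resolution. It does not remove the effect, because related AEs judged chronic or stable can also close without resolving.

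**The start-rule error is rare.** It needs a non-carry-over AE, collected under this protocol, with a missing start day in the dosing month and a stop before dosing. A reader might infer that nearly half of short AEs with a missing start day are affected. The calculation behind that gives 45% with dosing and onset dates uniform over a 30-day month, and 24% or 10% when pre-dose collection lasts only 7 or 3 days. The number of AEs with a missing start day is unknown, so no frequency can be stated.

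**First-of-month starts and end-of-month stops are a conservative convention.** This is accepted. A reader might infer that 6.4 always takes the longest possible duration, but the stop is capped at discontinuation and death, and the dosing-month rule can shorten.

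**Little depends on it.** The study gives access to treatment, tests no hypothesis, and lists all data with AE outcome. That limits the consequence; the duration tables would still be wrong where these rules apply.

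**Conclusion.** Two defects follow from the text of SAP 6.4 alone: the dosing-month start rule can give a duration of zero or less and move a pre-dose AE onto treatment, and the stop-date bullets contradict each other when only the year is known. The first probably touches few records.

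The third is a gap in the text that can be seen. If the safety section does not fill it and durations come from resolved AEs only, they are biased short for long-lasting toxicities: about 30, 38 or 53 days against a true 60 with 105, 180 or 730 days of treatment. These sizes rest on exponential durations, uniform onset and follow-up to 30 days after treatment. At the diarrhea resolution medians that the protocol reports from the Phase 3 study (1.5 days for all grades, 3.5 for Grade 2 or higher, 6 for Grade 3), the effect is negligible. A reader might infer that the longest events are always lost; the documents support only a tendency, strongest when treatment is short relative to the toxicity.

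**What to change.** - **Start date.** Add to SAP 6.4 that an imputed start may not fall after a known stop date, and that an AE whose known stop precedes Cycle 1 Day 1 stays classified as pre-dose. In the March example this gives 1 day, the shortest possible value and not an estimate of the true 6, so durations from imputed dates should be flagged. State also that the dosing-month rule overrides the first-of-month rule.
- **Stop date.** Reconcile the two bullets so that a missing month with a known year has one treatment.
- **Duration.** Define the AE duration formula in SAP 6.3.
- **Ongoing AEs.** Unless the safety section already does so, censor AEs without a stop date at the last AE follow-up date, report the number ongoing, and give the Kaplan-Meier median duration. Note that censoring at death or new therapy may be informative.

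The cost is SAP wording and minor programming. No new data are needed, since AE dates and outcome are already collected.
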